2.8 Early Biomarkers of Safety and Innate Immune Response

2.8.1 Microarrays

Objective: The objective is to evaluate the vaccine-induced modulation of transcriptome responses in blood transcriptional modules (BTMs), specifically the interferon and inflammatory BTMs.

The vaccine-induced modulation of transcriptome responses will be evaluated on whole blood samples collected at 5 time points: Day 1 (pre-vaccination and 6h after vaccination), Day 2 (24h after vaccination), Day 4 and Day 8. Base analysis will be performed using sets of coordinately regulated genes, or BTMs), as defined by Obermoser, G. *et al.* (2013).

Previously conducted analyses in a non-human primate model have shown that the inclusion of LDH153R in the formulation produces a significant upregulation of 3 BTMs (M1.2, M3.4 and M5.12) containing interferon stimulated genes at 24 hours after vaccine administration. Furthermore, the addition of LDH153R did not upregulate any of the BTMs containing proinflammatory genes (M3.2, M4.2, M4.6, M4.13, M5.1, M5.7 and M7.1).

Specifically, the aim is to show that the LHD153R adjuvant significantly upregulates the response of the interferon BTMs (M1.2, M3.4 and M5.12) but not the pro-inflammatory BTMs (M3.2, M4.2, M4.6, M4.13, M5.1, M5.7 and M7.1) in at least one LHD153R dosage group compared to the MenC control group at 24 hours post-vaccination.

Endpoints:

Vaccine Induced Modulation of Interferon and Pro-Inflammatory Transcriptional Modules

- a. The module-specific geometric mean response for each blood sampling time point. For each of the 10 BTMs (3 interferon, 7 pro-inflammatory), the subject level module response will be determined by computing the average log2 fluorescence intensity of genes belonging to the module at each blood sampling time point.
- b. The module-specific geometric mean fold change from baseline Day 1 to each postvaccination sampling time point. For each BTM, the subject-level fold change from pre-vaccination to each post-vaccination time point will be computed (ie, postvaccination value / pre-vaccination value). Module level responses will be computed by averaging the log2 scaled, subject-level fold-changes for each dosage group and blood sampling time point.

Vaccine Induced Transcriptome Responses

- c. Gene level fold change from baseline in transcriptome response for each gene at each post-vaccination blood sampling time point. In order to reduce the false discovery rate, the

initial set of genes will be reduced by applying a non-specific filtering to the pooled samples coming from all available dosage groups, including the control group. Only those genes showing a between subject interquartile range, in the log2transformed fold change from baseline, ≥ 0.5 will be retained. Analysis Methods:

- a. To evaluate the LHD153R ability to upregulate the expression level of a given BTM at a specified time point the following hypothesis needs to be tested for each BTM:

$$H_0: (\mu_{LHD153-12.5} \leq \mu_{MenC}) \text{ and } (\mu_{LHD153-25} \leq \mu_{MenC}) \text{ and } (\mu_{LHD153-50} \leq \mu_{MenC}) \\ \text{and } (\mu_{LHD153-100} \leq \mu_{MenC})$$

$$H_\alpha: (\mu_{LHD153-12.5} > \mu_{MenC}) \text{ or } (\mu_{LHD153-25} > \mu_{MenC}) \text{ or } (\mu_{LHD153-50} > \mu_{MenC}) \\ \text{or } (\mu_{LHD153-100} > \mu_{MenC})$$

The module response, fold change from baseline at the 24 hour time point, will be analyzed using analysis of variance (ANOVA) with the module response as the dependent variable and a fixed effect for dosage group. The adjusted (model-based) geometric mean fold changes, adjusted ratios of geometric mean responses between vaccine dosage groups and the corresponding two-sided, 95%, confidence intervals will be calculated based on this model. Should the data violate the normality assumption, then a Kruskal-Wallis test will be performed instead, followed by pairwise testing of the dosage groups in the same manner as previously described.

All 10 BTMs will be evaluated and the p-values adjusted using the BenjaminiHochberg False Discovery Rate (FDR) control procedure. BTMs with an adjusted pvalue ≤ 0.05 will be examined further.

- b. The module-specific geometric mean fold changes will be summarized using unadjusted geometric means and corresponding two-sided, 95% CIs by vaccine dosage group for each blood sampling time point. Summary statistics will be completed by providing minimum, maximum, first and third quartiles as well as the median.
- c. To identify transcriptional signatures which are correlated to serum bactericidal assay (SBA) titers, Spearman's rank correlation coefficients will be determined for each gene using the log2 gene-level fold change from baseline and the log2 transformed SBA titer at each post-vaccination time point. Genes will be ranked from largest magnitude to smallest magnitude of the correlation coefficient (ie, by the absolute value of the coefficient) and presented in rank order with the upper 10-th percentile identified for each post-vaccination time point.

Graphical Displays: The upregulation, or lack thereof, will be presented graphically for the modules being examined by dosage group.

Criteria for Assessment: This exploratory endpoint will be verified if the overall null hypotheses are rejected for at least 2 of the 3 interferon BTMs (M1.2, M3.4 and M5.12) and rejected for at most 2 of the 7 pro-inflammatory BTMs (M3.2, M4.2, M4.6, M4.13, M5.1, M5.7 and M7.1), with significance level $\alpha \leq 0.05$ (after correction for multiple testing), at the 24 hour post-vaccination time point.

As a hypothesis generating exercise, the same procedure will also be used for the other time points [Day 1 (6 hours), Day 4 and Day 8], in order to evaluate LHD153R effects at time points different from the 24 hours.

For innate transcriptome response predictive of hSBA, genes with a correlation coefficient above the 90-th percentile (as defined earlier) will be considered the most correlated genes, either positively or negatively. **Possible additional exploratory analyses:**

Additionally, the relationship between significant BTMs and solicited AEs may be evaluated by plotting the fold-change (y-axis) for subjects with a given severity of the solicited adverse event (x-axis) with vaccine group differentiated by symbol, color or grouping.

Functional enrichment analysis for those genes identified as correlated, or inversely correlated, to hSBA titers will be performed by testing all gene ontology terms and testing whether any category terms are over represented using the hypergeometric test.

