2. STATISTICAL CONSIDERATIONS

2.1 General

Because a maximum of 16 subjects per dosage group will participate in the exploratory endpoint analyses, sample sizes of 12 and 16 were considered. The table below provides the probability to observe at least 1 subject with an event for several presumed true frequencies within an individual dosage group (MenC-CRM₁₉₇ or MenC-CRM₁₉₇ plus an assigned-level of LHD153R/Al(OH)₃).

Table 2 Probability of Observing at Least 1 Subject with an Event

Frequency of Event	Probability to Observe at Least 1 Subject with an Event Given N	
	N=12	N=16
0.001	0.0119	0.0159
0.005	0.0584	0.0771
0.01	0.1136	0.1485
0.025	0.2620	0.3331
0.05	0.4596	0.5599
0.10	0.7176	0.8147
0.15	0.8577	0.9257
0.20	0.9313	0.9718
0.30	0.9862	0.9967
0.40	0.9978	0.9997

Distributions of antibodies are generally skewed to the right (Nauta, 2010). Therefore, prior to any statistical analysis that assumes normally distributed observations, antibody titers or concentrations will be log₁₀-transformed.

Concentrations and titers below the lower limit of detection (LLOD) will be set to half the LLOD for inclusion in summaries requiring a value.

Many analyses will be performed using SAS® Software version 9.1 or higher. Other software packages such as those available in R may also be used to perform analyses. Specifically, R version 3.1 or higher will be used; and, functionality will be extended through the use of the Bioconductor, and other packages (e.g., GO, plotrix, etc.).

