7. APPENDICES

Below is the CV% for each of the cytokine and chemokine assays.

Assay	CV%
IFN- γ	12.6
IL-10	10.0
IL-12p70	6.5
IL-13	16.4
IL-1 β	24.2
IL-2	16.4
IL-4	15.9
IL-6	6.7
IL-8	3.6
TNF- α	14.7
Eotaxin	8.5

Assay	CV%
MCP-4	9.0
MDC	9.5
MIP-1 α	8.7
MIP-1 β	12.8
TARC	8.4
GM-CSF	16.1
IL-12/IL-23p40	7.9
IL-15	6.1
IL-16	5.4
IL-17A	13.9
IL-1 α	16.0

16 NOV 17 Final Version 2.0

Confidential

Eotaxin-3	18.5	IL-5	32.4
IL-8 (HA)	11.5	IL-7	6.6
IP-10	10.9	TNF- β	15.7
MCP-1	11.2	VEGF	5.1

IFN = interferon; IL = interleukin; TNF- α = tumor necrosis factor – alpha; IP-10 = inducible 10-kilodalton (kDa) protein; MCP-1 = monocyte chemo-attractant protein – 1; MDC = macrophage-derived chemokine; MIP-1 α = macrophage inflammatory protein – 1 α ; TARC = thymus and activation-regulated chemokine; GM-CSF = granulocyte macrophage colony stimulating factor; TNF- β = tumor necrosis factor – beta; VEGF = vascular endothelial growth factor.

This section contains additional information related to weighting for summaries of innate cell phenotyping and activation. The expression of specific immune markers and co-stimulatory molecules of interest can be obtained from the weighting in these tables.

Myeloid and Lymphoid Phenotyping and Lymphoid Activation Weights

Myeloid Activation Weights

	HLADR	CD40	CD86	CD32	CD64	CD1c
Myeloid Activation						
CMo/HLADR+	1					
CMo/CD40+		1				
CMo/CD86+			1			
CMo/CD32+				1		
CMo/CD64+					1	
IMo/HLADR+	1					
IMo/CD40+		1				
IMo/CD86+			1			
IMo/CD32+				1		
IMo/CD64+					1	
NCMo/HLADR+	1					
NCMo/CD40+		1				
NCMo/CD86+			1			
NCMo/CD32+				1		
NCMo/CD64+					1	
cmDC CD1c+ /HLADR+	1					1

cmDC CD1c- /HLADR+	1					
cmDC CD1c+ /CD40+		1				1
	HLADR	CD40	CD86	CD32	CD64	CD1c
cmDC CD1c- /CD40+		1				
cmDC CD1c+ /CD86+			1			1
cmDC CD1c- /CD86+			1			
cmDC CD1c+ /CD32+				1		1
cmDC CD1c- /CD32+				1		
cmDC CD1c+ /CD64+					1	1
cmDC CD1c- /CD64+					1	
pDC /HLADR+	1					
pDC /CD40+		1				
pDC /CD86+			1			
pDC /CD32+				1		
pDC /CD64+					1	

CD4 CRM19740L+G-2-13-17-21-T-/CD4	CD4 SEB40L+G-2-13-17-21-T-/CD4
-----------------------------------	--------------------------------

The following tables present the genes that are included in the interferon and inflammation modules being considered for this study.

Genes Included in Module M1.1 - Interferon		
LY6E	OAS1	FLJ20035
IFIT1	MX1	IFITM3
OAS1	BATF2	IFIT3
IFIT1	LAMP3	CXCL10
IFIT3	IFI44L	EPSTI1
OAS3	XAF1	SERPING1
IFIT3	OASL	LOC26010
OAS1	IFI44	OAS2
OASL	OAS2	RSAD2
LOC129607	TRIM6	RTP4
ISG15	HES4	

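### The transcriptome rule states one-sided hypotheses but tests them with ANOVA or Kruskal-Wallis and counts rejections without regard to direction

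*SAP*

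**What the plan says.** All of this is in SAP Addendum 1, Section 2.8.1 Microarrays. The wording is the same in both copies of the addendum in the file.

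- **Aim.** It is directional: "Specifically, the aim is to show that the LHD153R adjuvant significantly upregulates the response of the interferon BTMs (M1.2, M3.4 and M5.12"; the seven pro-inflammatory modules should not rise. The comparison is at least one LHD153R dosage group against MenC at 24 hours.
- **Hypotheses.** Analysis Methods, item a, introduces them with the words "To evaluate the LHD153R ability to upregulate the expression level of a given BTM at a specified time point the following hypothesis needs". H0 is that all four LHD153R means are at or below MenC. The alternative is that at least one is above.
- **Test.** The module fold change "will be analyzed using analysis of variance (ANOVA) with the module response as the dependent variable and a fixed effect for dosage group". Model-based ratios between dosage groups with two-sided 95% confidence intervals are also planned. The fallback reads "Should the data violate the normality assumption, then a Kruskal-Wallis test will be performed instead"; pairwise tests come after it.
- **Multiplicity.** Benjamini-Hochberg across the 10 module p-values, with a cut-off of 0.05.
- **Decision rule.** "This exploratory endpoint will be verified if the overall null hypotheses are rejected for at least 2 of the 3 interferon BTMs" and for at most 2 of the 7 pro-inflammatory modules, at 24 hours. The same procedure is reused at 6 hours, Day 4 and Day 8 to generate hypotheses.
- **Display.** "The upregulation, or lack thereof, will be presented graphically for the modules being examined by dosage group".

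**The concern.** The hypotheses have a direction and the named tests do not. An overall F-test or a Kruskal-Wallis test rejects when any groups differ: when doses lie below MenC, or when doses differ only among themselves. Neither is a valid test of the printed H0, and nothing in the rule restores the direction.

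The error can go either way:

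- Down-regulated interferon modules count towards verification, although H0 is true for them.
- Down-regulated pro-inflammatory modules count against verification, although the aim is only that they should not rise.

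At stake is the formal statement that LHD153R raises interferon modules without raising inflammation modules. It does not touch the primary or secondary analyses or the dosage selection.

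**Working it through.** **Inputs.** There are five groups (MenC and four LHD153R doses). Section 2.1 of the addendum gives the group sizes: "Because a maximum of 16 subjects per dosage group will participate in the exploratory endpoint analyses, sample sizes of 12 and 16 were considered". The 10 modules, the 0.05 cut-off and the 2-of-3 and 2-of-7 counts come from Section 2.8.1. The addendum gives no SD, effect size, correlation or power for this rule, so there is no stated figure to reproduce. Effects below are assumed, in SD units of the module response, with normal data and equal variances.

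**Step 1: one module, exact.** Let all four doses lie 1 SD below MenC, so H0 is true. The group means are 0, −1, −1, −1, −1, with overall mean −0.8. The non-centrality of the F-test is

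λ = n × [0.8² + 4 × 0.2²] = n × 0.80,

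which is 12.8 for n = 16 (df 4, 75) and 9.6 for n = 12 (df 4, 55). The probability of rejecting at 0.05 is **0.803** and **0.653**. Reversing every sign leaves λ unchanged, so the test behaves identically for an increase.

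**Step 2: one module, simulated, n = 16, nominal 0.05, H0 true in every row.** The directional comparator is the one-sided Dunnett test: the largest of the four statistics (dose mean − MenC mean) / (s√(2/n)), referred to its distribution under equal means.

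| True pattern | F | Kruskal-Wallis | One-sided Dunnett |
|---|---|---|---|
| All doses −0.5 SD | 0.25 | 0.23 | 0.001 |
| All doses −1 SD | 0.81 | 0.77 | <0.001 |
| Equal steps down to −1 SD | 0.68 | 0.66 | 0.002 |
| One dose only −1 SD | 0.80 | 0.75 | 0.04 |

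**Step 3: the full rule.** Ten modules, exchangeable correlation 0.3, Benjamini-Hochberg at 0.05, then the two counts; 10,000 runs per scenario. Entries are the probability of *verified* for n = 16, with n = 12 in brackets.

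| Interferon modules | Inflammation modules | Overall F | One-sided Dunnett |
|---|---|---|---|
| −1 SD, all doses (H0 true) | no effect | 62% (37%) | 0% |
| −0.75 SD, all doses (H0 true) | no effect | 23% (12%) | 0% |
| −1 SD at 50 and 100 µg only (H0 true) | no effect | 90% (68%) | at most 0.1% |
| +1.5 SD, all doses | −1 SD, all doses | 8% (23%) | 99.9% (99%) |
| +1.5 SD, all doses | −0.5 SD, all doses | 83% (87%) | 99.9% (99%) |
| +0.75 SD, all doses | no effect | 23% (12%) | 52% (34%) |
| Equal steps up to +1 SD | no effect | 43% (23%) | 59% (39%) |
| +1 SD, top dose only | no effect | 62% (38%) | 51% (32%) |

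Under F, the first row hardly depends on the correlation: 59–64% (35–38%) for correlations from 0 to 0.6. The fourth row ranges over 2–14% (13–31%). With no effect in any module, both tests give at most 0.3%. Independent repeats of the main scenarios agreed to within about 1–2 percentage points.

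**The case against.** The strongest reply is that direction is already in the rule. It counts rejections of the overall null hypotheses, and those are printed as one-sided, so a rejection is by definition a claim of up-regulation. That is true of the hypotheses. But the tests named to reject them have no direction, and no one-sided contrast is named as the source of the adjusted p-values. Part of this stands: since the p-value is never identified, the error rates above apply to the overall-p-value reading. The Kruskal-Wallis fallback, itself an overall test, supports that reading.

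Second, ratios with confidence intervals, pairwise tests and graphs are planned, so a reader would notice a verified label on modules that had fallen. This also stands, but none of these outputs enters the Benjamini-Hochberg step or the count.

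Third, the effects are assumed, and the non-human primate results quoted in Section 2.8.1 point to an interferon increase at 24 hours. A small fall does limited damage: 0.5 SD down at all doses gives about 5% verified at n = 16 and 2% at n = 12. In the hoped-for case (interferon +1.5 SD at all doses, inflammation unaffected) the choice of test barely matters at n = 16: 99% for both, and 92% against 98% at n = 12. However, the rule also fails when interferon rises and inflammation falls, and it loses power when all doses respond moderately.

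Fourth, Dunnett is not uniformly better. It loses when only the top dose responds, which is a plausible pattern in a dose-escalation study. This stands and is reflected in the fix.

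**Conclusion.** The concern holds. Section 2.8.1 states one-sided hypotheses, names tests that cannot address them, and bases a yes/no criterion on the count of rejections. On the natural reading, verified can be declared in most trials when every printed H0 is true (62% at n = 16 with interferon 1 SD down at all doses). It can also be withheld in most trials that meet the stated aim (8% verified with interferon +1.5 SD and inflammation −1 SD). The sizes depend on the assumed effects. The blindness to sign does not, since the F-test's non-centrality is the same for an increase and a decrease of equal size.

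This should be fixed before the rule is applied. Because the endpoint is exploratory, the consequence is confined to the mode-of-action conclusion.

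A separate labelling point: the rule names interferon module M1.2, but the matching list in Section 7 of the addendum is headed "Genes Included in Module M1.1 - Interferon". One of the three modules that decide the endpoint therefore has no gene list under its own name.

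**What to change.** Keep the ANOVA model and state in Analysis Methods, item a, that each module's p-value is the one-sided Dunnett p-value for the largest of the four LHD153R-minus-MenC contrasts. Name a one-sided rank-based many-to-one test as the fallback in place of Kruskal-Wallis. Apply Benjamini-Hochberg to those 10 p-values and report which dosage group drives each rejection.

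If sensitivity to a top-dose-only response matters more, keep the overall p-value in the Benjamini-Hochberg step but count a rejection only when at least one LHD153R/MenC ratio has its lower 95% confidence limit above 1. In the same simulations this gives verified in 0% with interferon 1 SD down at all doses and 1.2% (1.2%) with only 50 and 100 µg down. Power for a top-dose-only +1 SD response is 58% (34%). It is not an exact test of the printed H0.

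In either case, make the rule and the gene list name the same module, M1.1 or M1.2.

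The cost is addendum wording and one option in the existing model; no new data are needed. With Dunnett, down-regulation becomes descriptive only, and power for a top-dose-only +1 SD response falls from 62% to 51% at n = 16 and from 38% to 32% at n = 12.

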2.8.2 Cytokines and Chemokines

Objective: To evaluate biomarkers that may be predictive of safety and/ or innate immune activation.

The vaccine-induced production of inflammatory cytokines and chemokines will be evaluated on serum samples using a commercially available multiplex electrochemiluminescence immunoassay for a panel of pro-inflammatory cytokines and chemokines. Cytokines and chemokines will be measured from serum collected at 5 time points: Day 1 (pre-vaccination and 6h after vaccination), 24h after vaccination (Day 2), Day 4 and Day 8.

There is no formal statistical hypothesis associated with this objective. However, based on pre-clinical results in non-human primates, inducible 10-kilodalton (kDa) protein (IP-10) concentrations at early time points may be detected at higher levels compared to baseline values of each subject. Further, different levels of serum chemokines and cytokines are expected in human healthy donors (Biancotto, et al, 2013). The kinetics of soluble mediators will be evaluated from baseline to early time points (up to Day 8) in serum. In each subject, cytokine and chemokine concentrations measured at different time points after vaccination will be compared to their baseline levels.

Table 4 List of Cytokines and Chemokines in Plasma by Multiplex (pg/mL)

Assays (units)	List of soluble mediators or markers of cellular effectors
Chemokines indicating activation of immune response which stimulate cell recruitment	
	Eotaxin, Eotaxin-3 MCP-1; MCP-4 MDC MIP-1 α ; MIP-1 β TARC IP-10 IL-8
Cytokines indicating a general activation of the immune system	
Proinflammatory c	GM-CSF IL-1 α ; IL-2; IL-5; IL-7; IL-12/IL-23p40; IL-15; IL-16 TNF- β VEGF-A Cytokines indicating activation of the innate immune system
	IFN- γ IL-1 β ; IL-4; IL-6; IL-8; IL-10; IL-12 p70; IL-13; IL-17A TNF- α

MCP-1 = monocyte chemo-attractant protein – 1; MIP-1 α = macrophage inflammatory protein – 1 α ; MDC = macrophage-derived chemokine; TARC = thymus and activation-regulated chemokine; IP-10 = inducible

10kilodalton (kDa) protein; IL-8 = interleukin – 8; IFN- γ = interferon gamma; GM-CSF = granulocyte macrophage colony stimulating factor; TNF- β = tumor necrosis factor – beta; VEGF-A = vascular endothelial growth factor – A.

Endpoint(s):

- a. The number and percentage of subjects with evaluable concentrations at or above the lower limit of detection (LLOD), as well as below the LLOD for each cytokine/chemokine for each dosage group and blood sampling time point.
- b. Cytokine and chemokine geometric mean concentrations for each dosage group and blood sampling time point.
- c. Subject level fold change from baseline in the concentration for each cytokine/chemokine for each post-vaccination blood sampling time point.

Analysis Method:

- a. The percentage of subjects above and below LLOD and associated two-sided 95% Clopper-Pearson CIs will be summarized by dosage group for each cytokine/chemokine at each blood sampling time point.
- b. Cytokine and chemokine geometric mean concentrations will be summarized using unadjusted geometric means and corresponding two-sided, 95% CIs by vaccine dosage group for each blood sampling time point. Summary statistics will be completed by providing minimum, maximum, first and third quartiles as well as the median.
- c. Change from baseline in the concentration of each cytokine and chemokine (subjectlevel fold change) will be summarized using unadjusted geometric means and corresponding two-sided, 95% CIs by vaccine dosage group for each post-vaccination blood sampling time point. Summary statistics will be completed by providing minimum, maximum, first and third quartiles as well as the median.

Graphical Displays: For each cytokine or chemokine with detectable levels, plot the mean concentration level over time for each group, indicating each dosage group with a symbol, color, or line type.

Additionally, for each cytokine or chemokine with detectable levels, plot the cumulative percentage of subjects with at least an n -fold change over baseline (n ranges from the minimum to maximum fold change across all time points) for each time point, indicating each dosage group with a symbol, color or line type.

Criteria for Assessment:

- a. Geometric mean fold rises and corresponding CIs will be used to determine which cytokines and chemokines have higher concentrations as compared to baseline concentrations.
- b. To evaluate differences in geometric mean ratios (GMRs) among the dosage groups, a Kruskal-Wallis test will be performed for each time point. If significant, then pairwise comparisons of the dosage groups will be performed with no adjustment for multiple comparisons. This is to identify any chemokines or cytokines that may be predictive of safety and/or innate immune activation.
- c. To evaluate differences in proportions of subjects with at least a two-fold change from baseline among the dosage groups, a test will be performed for each postvaccination time point. If significant, then pairwise comparisons of the dosage groups will be performed with no adjustment for multiple comparisons.

d. To evaluate differences among the dosage groups in the empirical cumulative distribution functions (eCDFs) of the proportions of subjects with at least an n -fold change over baseline, the Kolmogorov-Smirnov test will be performed. If significant, then pairwise comparisons of the eCDFs will be performed using the two-sample Kolmogorov-Smirnov test.

Possible additional exploratory analyses:

If the number of observations with measurable levels permit, the kinetics of the soluble mediator(s) will be evaluated from baseline up to day 8 post-vaccination in serum.

Should LHD153 have detectable levels also, a graphical representation of the correlation between the any cytokine/chemokine with measurable levels and the LHD153 concentration will be generated with dosage group differentiated by symbol, color or line type.

If differences or trends in solicited AEs between vaccine dosage groups are observed, then the relationship between chemokine/cytokine concentrations and solicited AEs at a given time point may be evaluated by plotting the concentrations of the chemokine/cytokine (yaxis) with the severity of the solicited adverse event (x-axis) with vaccine dosage group differentiated by symbol, color or grouping.

Appendices include information about the derivation of the LLODs.

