8.7.2 Immunogenicity

Values below the limit of quantification (recorded as “< LLQ”) will be set to half the lowest limit of quantification.

Titer greater or equal to a given threshold is defined as a binary variable for nonmissing values as:

= 1, if the titer is superior or equal to the given threshold (\geq 4-fold rise in hSBA titer),

= 0, otherwise.

Seroresponse is defined as a binary variable for subjects with non-missing values prevaccination and postvaccination as:

- For subjects with a prevaccination hSBA titer < 4:

= 1, if postvaccination titer \geq 8

- For subjects with a prevaccination hSBA titer ≥ 4 :

= 1, if post-vaccination titer increases at least 4 times the baseline hSBA titer

= 0, otherwise.

Geometric Mean Titer/Concentration

The GMT/GMC will be calculated using the following formula:

$$\text{GMT} = \sqrt[n]{t_1 t_2 \dots t_n} = \sqrt[n]{\log_{10}(t_1) + \log_{10}(t_2) + \dots + \log_{10}(t_n)} = 10^{\frac{1}{n} \sum_{i=1}^n \log_{10}(t_i)}$$

where t_1, t_2, \dots, t_n are n observed immunogenicity titers/concentrations.

Geometric Mean Ratio

Geometric mean ratios (GMRs) measure the changes in immunogenicity titers/concentrations *within* subjects.

The GMR will be calculated using the following formula:

$$\text{GMR} = \frac{\sqrt[n]{\log_{10}(v_{ij}) + \log_{10}(v_{ik})}}{\sqrt[n]{\log_{10}(v_{ij})}} = \frac{\sqrt[n]{\log_{10}(v_{ij}) + \log_{10}(v_{ik})}}{\sqrt[n]{\log_{10}(v_{ij})}} = 10^{\frac{1}{n} \sum_{k=1}^n \log_{10}(v_{ik}) - \frac{1}{n} \sum_{j=1}^n \log_{10}(v_{ij})}$$

where, for n subjects, v_{ij} and v_{ik} are observed immunogenicity titers/concentrations for subject i at time-points j and k , $j \neq k$.

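### Cytokine two-fold criterion: with undetectable values set to half the LLOD, any move from undetectable to detectable counts as a two-fold change without needing a real two-fold rise

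*SAP*

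**What the plan says.** All references are to SAP Addendum 1, version 2.0, unless stated otherwise.

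- Section 2.1: "Concentrations and titers below the lower limit of detection (LLOD) will be set to half the LLOD for inclusion in summaries requiring a value".
- Section 2.8.2, endpoint a, treats a value equal to the LLOD as detectable (at or above).
- Section 2.8.2, endpoint c: "Subject level fold change from baseline in the concentration for each cytokine/chemokine for each post-vaccination blood sampling time point".
- Section 2.8.2, criterion c, plans a test at each post-vaccination time point: "To evaluate differences in proportions of subjects with at least a two-fold change from baseline among the dosage groups". If that test is significant, "pairwise comparisons of the dosage groups will be performed with no adjustment for multiple comparisons".
- Section 2.8.2, criterion d, compares the n-fold distributions by the Kolmogorov-Smirnov test, and the graphs show the same n-fold curves.

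Section 2.8.2 has no separate rule for an undetectable baseline and sets no minimum post-vaccination value. Its restriction to detectable levels is written for the graphs only, and it applies by analyte, not by subject. The half-LLOD rule is not repeated there. It reaches criterion c through section 2.1, because a ratio requires a value and no other rule is given.

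**The concern.** A fold-change cut-off should ask the same of every subject. Here the hurdle depends on which side of the LLOD the baseline falls. A subject with a true baseline of 0.99 x LLOD is counted at a later value of 1.00 x LLOD, a rise of about 1%. A subject at 1.01 x LLOD must reach 2.02 x LLOD. For undetectable baselines the criterion therefore measures whether the analyte became detectable, which endpoint a already reports.

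At stake is the comparison of early cytokine response between dosage groups. Measurement error around the LLOD produces counted subjects in every group, MenC included, and so dilutes a true dosage difference. The groups have at most 16 subjects.

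**Working it through.** The plan gives no expected rate for this criterion, so there is no stated figure to reproduce.

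**Inputs from the addendum.** Substituted value 0.5 x LLOD (section 2.1). Cut-off: ratio of at least 2 (2.8.2, criterion c), read as a rise. Detectable means at or above the LLOD (2.8.2, endpoint a). Assay CVs (section 7) run from 3.6% (IL-8) to 32.4% (IL-5); the median of the 30 listed is 11.05%. Group size is at most 16 (section 2.1).

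**Step 1, algebra.** With one LLOD for both samples, the smallest ratio for a subject who goes from undetectable to detectable is LLOD / (0.5 x LLOD) = 2. The cut-off is inclusive, so every such subject is counted.

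**Step 2, false rate at a fixed true level.** Model with no true change: baseline and later value are each r x LLOD x exp(s z), with independent standard normal z and s = sqrt(ln(1 + CV²)). At r = 1 each sample is below the LLOD with probability one half, so the rate is 0.5 x 0.5 = 25% at any CV, apart from a negligible addition at high CV. By simulation:

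| True level | CV 10% | CV 16% | CV 30% |
|---|---|---|---|
| 1.0 x LLOD, as planned | 25% | 25% | 25% |
| 0.9 x LLOD, as planned | 12% | 19% | 23% |
| 1.0 x LLOD, later value must reach 2 x LLOD | 0.0% | 0.0% | 0.6% |

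Without any substitution, error alone gives a ratio of at least 2 in 0.1% of pairs at CV 16% and 4.8% at CV 30%. Most of the planned rate therefore comes from the rule.

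**Step 3, false rate over a population.** The documents give no concentrations, so the spread of true levels is an assumption: log-normal with geometric SD 2, and the median varied.

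| Median true level | CV 11%, as planned | CV 16%, as planned |
|---|---|---|
| 0.5 x LLOD | 2.2% | 3.1% |
| 1 x LLOD | 3.5% | 5.1% |
| 2 x LLOD | 2.2% | 3.2% |
| 5 x LLOD | 0.25% | 0.5% |

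Requiring 2 x LLOD for undetectable baselines brings these rates to 0.0% at CV 11% and to at most 0.1% at CV 16%.

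**Step 4, in subjects.** For a group of 16 with the median at the LLOD: 16 x 0.035 = 0.56 false counts at CV 11%, and 16 x 0.051 = 0.82 at CV 16%. Only if every subject sat exactly at the LLOD would it be 16 x 0.25 = 4.

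**The case against.** The case for leaving the rule alone is mainly about consequence, and much of it stands. Section 2.8.2 says that no formal hypothesis attaches to this objective. Criterion c is one of four. The planned at-or-above-LLOD percentages would let a careful reader see when a two-fold count merely reflects crossing the limit. Analytes well above the LLOD are hardly affected, and the 25% is a worst case. None of this removes the misclassification for analytes near the limit.

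Three stronger readings are tempting, and the documents do not support them.

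- A reader might infer that the counted subjects had no real rise. An undetectable baseline can lie far below the LLOD, so some of them did rise two-fold or more. What fails is that the rule does not require it.
- A reader might take the hSBA seroresponse rule (main SAP, section 8.7.2) as proof that the plan avoids unequal hurdles elsewhere. For a titer below 4 it asks for 8; at 4 it asks for 4 x 4 = 16. A value just under 4 thus needs about a two-fold rise and a value of 4 needs a four-fold rise. That rule has a step of its own and is not a clean contrast.
- A reader might conclude from the LOD tables that run-to-run differences make matters much worse. The listed IL-13 LODs run from 0.864 to 14.858 (14.858 / 0.864 = 17.2-fold), but one run drives this; the other six lie between 0.86 and 2.03. Section 2.8.2 refers to the appendices for how the LLODs were derived, and that text is not fully available here. Whether run-specific or common LLODs apply cannot be judged.

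**Conclusion.** The point holds in limited form. Followed as written, sections 2.1 and 2.8.2 count every move from undetectable to detectable as a two-fold change when both samples share one LLOD. The false rate is up to 25% for a true level at the LLOD. Over the assumed populations it is about 2-4% (CV 11%) and 3-5% (CV 16%) for medians of 0.5 to 2 x LLOD, and 0.5% or less at 5 x LLOD.

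These rates assume no true change and independent log-normal error, with the listed assay CV taken as the total error. The geometric SD of 2 is also an assumption. Errors of equal frequency in all groups blur dosage differences; the documents give no basis for saying that they favour one dosage. Because the endpoint is exploratory and only low-abundance analytes are affected, this is a cheap improvement and no threat to the trial's main conclusions.

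**What to change.** In section 2.8.2:

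- Criterion c: if the baseline is below the LLOD, count the subject only when the post-vaccination value is at least 2 x LLOD; otherwise require post/baseline of at least 2.
- Criterion d and the n-fold cumulative plots: set both baseline and post-vaccination values below the LLOD to the LLOD, so that an undetectable-undetectable pair has ratio 1. Raising the baseline alone would not do. With the later value left at half the LLOD, each such pair would become a false 0.5-fold fall.
- Keep half the LLOD for the geometric mean concentrations.
- State that the same LLOD is used for both samples of a ratio.

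Flooring both samples at the LLOD and then applying the two-fold cut-off gives the same classification as the criterion c rule, so one derived ratio can serve both criteria.

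The cost is a few sentences in the addendum and a change to the derivation program. The downside is that a true rise from undetectable to between 1 and 2 x LLOD is no longer counted as two-fold. It remains visible in the at-or-above-LLOD percentages already planned under endpoint a.
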